## 1.0 Project Summary/Abstract

Depression and anxiety are the leading causes of disability and lost productivity, and are often underdiagnosed and undertreated owing to access, cost, and stigma barriers. Novel and scalable psychotherapies are urgently needed. Advances in artificial intelligence (AI) offer a transformative opportunity to develop intelligent voice assistants as virtual health agents accessible on personal devices. Meanwhile, major advances in human neuroscience have fueled a paradigm shift to study brain mechanisms underlying behavioral health interventions. Leveraging emerging science in these transdisciplinary areas, this project aims to develop and rigorously test a novel voice-enabled, AI virtual agent named Lumen, trained on Problem Solving Therapy (PST), for patients with moderate, untreated depressive and/or anxiety symptoms. The project will investigate the effect of Lumen on engagement of a priori neural targets—amygdala for emotional reactivity and dorsal lateral prefrontal cortex (DLPFC) for cognitive control—as putative mechanisms. The project has 2 phases: R61 and R33 (see Figure 1). Phase 1 is the R61 phase (years 1-2) and will be the sole focus of this protocol. Focusing on Lumen development and refinement as well as pilot testing, Phase 1 has 2 specific aims. Aim 1 on Lumen development and refinement will proceed in 2 stages: (1) scenario-based clinician evaluations, and (2) a formative user study (n=30 participants). Aim 2 is to pilot test Lumen in a 2-arm randomized clinical trial (pilot RCT), among 60 participants with moderate, untreated depression and/or anxiety who are randomized in a 2:1 ratio to receive PST with Lumen (n=40) on a secure study iPad or be on a waitlist (n=20). At weeks 0 and 16 participants will complete functional magnetic resonance imaging (fMRI) to assess neural target engagement as well as validated surveys of patient-reported outcomes (PROs) (e.g., depressive and anxiety symptoms, functioning, quality of life). In addition, participants will complete ecological daily assessments of mood, stress, appraisal and coping for 7 days every 2 weeks during the 16-week follow-up period. The Phase 1 milestones are (1) establishing the functionality, usability, and treatment fidelity of Lumen; and (2) demonstrating feasibility, acceptability, and neural target engagement. Achieving these milestones will provide the basis for the future R33 phase (Phase 2) focused on examining target engagement and PROs in a larger 3-arm RCT by comparing Lumen with a waitlist control arm and an in-person PST arm. This protocol only focuses on the R61 phase.

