#### Aim 2: Pilot RCT

**Pilot RCT.** After teleorientation, RCT participants are scheduled for a baseline assessment visit. During the baseline visit, a trained study coordinator performs fMRI screening and data acquisition and collects baseline data per standardized measurement protocols. Females of child-bearing age who indicate any possibility that they may be pregnant must take a point-of-care urine pregnancy test. At the end of the baseline visit participants receive instructions to complete the initial ecological daily assessment for the next 7 days. Following successful completion of the baseline measures, fully eligible, consented participants are randomized to either Group A (Lumen Intervention) or Group B (waitlist control), at a 2:1 allocation.

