**Protection against accidental recording.** Accidental recording is a commonly raised concern regarding voice-enabled technologies. In the case of Lumen, the application is installed on the locked-down and encrypted study iPad. In order to prevent accidental recording, the following protections are implemented: First, the iPad has a keypad lock. Recording takes place only in the unlocked mode, after the participant opens the Alexa app, and gives permission verbally (using specific “wake phrases” such as “Launch Lumen Session,” or by tapping the option on the iPad screen. Second, participants are informed that all Lumen sessions are recorded and give explicit permission for this as part of their informed consent process. Third, if the study iPad is left unattended during an active session, the iPad locks after 10-seconds, and after 30 seconds of no verbal input from the participant, the Lumen session shuts down (preventing any further recording). Once the participant returns, they must go through the process of unlocking iPad and waking Lumen to actively resuming their session.

**Potential benefits to participants.** Eligible participants in the study have mild or moderate depressive and/or anxiety symptoms that are not treated. They receive PST by interacting with Lumen on a secure study iPad. Waitlist controls have the option to receive Lumen after their 16-week assessments. PST is a brief skill-enhancing psychotherapy with robust evidence for efficacy in treating depression and anxiety. PST focuses on improving one’s skills involved in solving personal real-life problems and is easy for most people to understand. Its stepwise, patient-driven approach is also easy to follow. Lumen is a voice-enabled, PST-trained agent who will undergo iterative design development and refinement based on information gathered from evaluation cycles and rigorous testing. Through interacting with Lumen, participants in the study may benefit from having PST at their fingertips and experience improvements in psychological symptoms, functioning and quality of life. If shown successful in this developmental R61 phase of the project, Lumen will undergo further confirmatory testing (in the R33 phase) and may downstream carry the potential to be scaled for use by people with depression and/or anxiety who cannot or will not seek professional help or who desire as-needed, personal help beyond what conventional treatment models can offer.

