## Aim 2: Pilot RCT

The study coordinators are trained on data collection according to standardized protocols, and their performance is continuously monitored. The following types of data are collected.

1. Data on diagnoses, prescriptions, clinical encounters, and hospitalizations are abstracted from EHR for eligibility screening and baseline characterization.
2. fMRI data and physical measurements are collected at the UIMC Advanced Imaging Center.
3. Survey data and ecological daily assessments are collected using self- and interviewer-administered questionnaires on REDCap, a HIPAA-compliant server.
4. With participant's explicit permission, PST sessions are audiorecorded and are stored in study configured accounts on the AWS cloud, accessible only by study staff.

See Appendix 2 for the list of study measures and assessment schedule.

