## 11.0 Data and Safety Monitoring

The following Data and Safety Monitoring Plan (DSMP) will be followed to ensure the safety of study participants and the validity and integrity of data in compliance with NIMH requirements.

**Independent Oversight.** Because the risks for adverse events (AEs) and data breaches are minimal in the pilot RCT, and the study is not a Phase III clinical trial, it is determined that a Data and Safety Monitoring Board (DSMB) is not needed. Instead a safety monitor *independent of* the study is responsible for overseeing the implementation of this DSMP to ensure (1) the protection and safety of human subjects and (2) the validity and integrity of the trial. [name], MD, o at the University of Illinois at Chicago (UIC), serves in this role. The safety officer is responsible for examining aggregate data on

recruitment and retention, adverse events (unexpected or serious), and subject complaints, but he will not be reviewing individual, identifiable, subject data. If unexpected or serious adverse events occur, these will be reported to the IRB in the form of Prompt Reports. See further details below.

Contact PI [name] and senior biostatistician [name], both of whom will be blinded during the pilot RCT, meet with [name] every 6 months during active participant recruitment and follow-up to present and discuss data and safety monitoring information (below). For the annual continuing renewal application to the IRB and the annual progress report to the sponsor each year, [name] will provide a summary of her findings and recommendations regarding the following:

- ascertainment and any actions to be taken in response to AEs and SAEs reported during the study
- reports related to study operations and the quality of the data
- possible modifications in the study protocol concerning recruitment, participant retention, data quality, or trial operations more generally.

**Safety Monitoring.** As in any clinical trial, it is not possible to anticipate all possible AEs. Staff will undergo extensive training in ascertaining, monitoring, and documenting AEs—serious or not. The study investigators have extensive experience in clinical trial organization and management, including data and safety monitoring for single site and multisite trials. Established procedures for rendering first aid and life-threatening emergencies will be monitored by [name] (psychiatrist).

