An AE is defined as any untoward medical or psychological event experienced by a patient during or as a result of his/her participation in the study that represents a new symptom or an exacerbation of an existing condition whether or not considered study-related based on appropriate medical judgment. SAEs are any adverse experience that results in any of the following outcomes:

- Death
- Life-threatening event/illness
- Inpatient hospitalization or prolongation of existing hospitalization
- Persistent or significant disability/incapacity
- Pregnancy resulting in a congenital anomaly/birth defect
- Any event requiring medical or surgical intervention to prevent permanent impairment or damage. In this study, this is defined as physician confirmed diagnosis of any of the following: angina pectoris, heart attack, stroke, transient ischemic attack, heart failure, coronary angioplasty or bypass surgery, peripheral vascular disease, , any other serious injury to the bone or muscle, liver failure, kidney failure, and cancer (except for non-melanoma skin cancer).

Non-serious AEs are all adverse events that do not meet the above criteria for “serious.” To ensure unbiased ascertainment, AEs will be systematically identified by querying participants at 16-week follow-up visits using the AE Patient Query Form. In order to access the electronic medical record, as needed, for AE adjudication, consenting participants are asked to provide and/or confirm the minimum necessary identifiers including first and last name, date of birth, mailing address, and whether they have received care at UI Health.

**Blinded Reporting.** In the pilot RCT, safety information will be monitored while keeping the true identity of the study groups masked. In his role as the study physician, [name] may need to become unblinded. But Contact PI [name] and biostatistician [name] as well as the independent safety monitor [name] will be blinded throughout the study and will review summaries of the numbers and rates of all AEs by blinded treatment group. Proper blinding of the other investigators and outcome assessors will be enforced as well.

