Treatment acceptability	Session metrics : Number and duration of PST sessions completed; End-of-session Lumen user survey : NASA Task Load Index (TLX),  User Experience Questionnaire-Short version (UEQ-S),  adapted Working Alliance Inventory for digital interventions (WAI-Tech) 			NA	NA	X
Digital health literacy	Digital Health Literacy Instrument 	self-report		X	NA	NA
COVID impact	COVID impact survey 	self-report		X	NA	NA
Religious involvement	Duke University Religion Index 	Self-report		X	NA	NA
COVID impact on social functioning	COVID impact on social functioning survey	self-report		X	X	NA
Social network	Social Network Index 	Self-report		NA	NA	X
Loneliness	UCLA 3-item loneliness survey 	Self-report		NA	NA	X
Height	Height	Measured		X	NA	NA
Weight	Body weight	Measured		X	X	NA
Blood pressure	Blood pressure	Measured		X	X	NA
Sociodemographics	age, sex, race, ethnicity, education, race, ethnicity, income, household size, marital status, employment status, occupation, smoking/vaping	self-report		X	NA	NA
Adverse Events (AE)	AE form	Interview		X	X	NA

aTo minimize missing data, participants will receive \$50 at wk 0, study iPad (unlocked) or \$100 (if opting out iPad) at wk 16, and \$1 per daily diary.

bHADS is used as the independent outcome measure of depressive and anxiety symptoms at weeks 0 and 16. PHQ9 and GAD7 are used for 2 purposes: (1) eligibility screening (before week 0) and (2) treatment progress monitoring across PST sessions (in weeks 1, 2, 3, 4, 6, 8, 10, 12).

cIn addition to ecological daily assessments that will occur for 7 days at weeks 0 and 16, they also will occur every 2 weeks (on weeks 2, 4, 6, 8, 10, 12). During active treatment in the Lumen arm (Studies 1 & 2) or the in-person PST arm (Study 2), this will occur for 3 days prior to, the day of, and 3 days after each scheduled PST session. For waitlist controls, this will occur for 7 days starting on Sunday of each assigned week.

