#### **B.4. Intention to Treat (ITT) and Handling Missing Data**

Clinical trials such as the one proposed must face the issues of dropout and missing data. We have put in place a strong plan to ensure maximum retention of participants through the course of the study, with a projected 85% or greater retention (see the *Recruitment and Retention Plan*). Data missing completely at random (MCAR) may be analyzed “as is” without imputation, as it does not introduce bias into estimates and inferences. More commonly, data are missing at random (MAR) owing to covariate-dependent events (e.g., irregular work shifts, children’s illness, transportation, and scheduling foul-ups). Our primary analysis technique, linear mixed models, is robust for MAR and provides unbiased estimates of model parameters without imputation. (One may impute as well, but the benefit is usually modestly improved power rather than changes to conclusions.) The more serious concern for behavioral interventions is the possibility that data will be missing not at random (MNAR). This occurs when dropout or missingness is related to the level of the outcome of interest (e.g., a participant’s level of depression or anxiety). If treatment is working well and symptoms of depression and anxiety have lessened, then participants may feel continuation in treatment is not necessary or beneficial. They drop out or miss sessions because the treatment seems to have worked. On the other hand, if participants experience no improvement in symptoms, they may drop out or miss sessions because they are discouraged that the treatment seems not to have worked. In either case, the loss of data is related to the outcomes under study and has the potential to bias the study’s conclusion about the intervention. Handling the problem of MNAR is difficult. First, there is no test for the presence of MNAR (*vs.* MAR). Second, there are many possible underlying sources of MNAR and there is no guarantee that explorations of missing data patterns will clearly reveal those sources. Third, missing data imputation for MNAR necessarily makes strong and untestable statistical assumptions, so that conclusions from imputed MNAR datasets must remain tentative. This picture reinforces our strong commitment to participant retention (see the Study 1 *Recruitment and Retention Plan*).

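### The only AE query scheduled after randomization depends on attending Visit 2, and none follows waitlist participants' use of Lumen

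*Combined protocol and SAP*

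**What the plan says.** Section 11.0 of the protocol gives one systematic method of finding adverse events: "To ensure unbiased ascertainment, AEs will be systematically identified by querying participants at 16-week follow-up visits using the AE Patient Query Form". Appendix 2 schedules the AE form, by interview, at weeks 0 and 16 and marks weeks 1 to 12 as not applicable. Section 5.0 puts the baseline visit before allocation: "Following successful completion of the baseline measures, fully eligible, consented participants are randomized". Section 6.0 has one assessment visit after baseline, and Appendix 4 places it at day 112 ± 14.

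The medical record has a limited role. Section 8.0 says: "Data on diagnoses, prescriptions, clinical encounters, and hospitalizations are abstracted from EHR for eligibility screening and baseline characterization". After baseline, Section 11.0 allows access when it is needed to adjudicate an event.

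On retention, Appendix 3, B.4 plans "with a projected 85% or greater retention".

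On the control arm, Section 7.0 says: "Waitlist controls have the option to receive Lumen after their 16-week assessments". The same section treats that use as coming after the study has ended. Section 11.0 has the safety monitor meet the study team "every 6 months during active participant recruitment and follow-up". Its AE definition covers events that occur during participation and also events that result from it.

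**The concern.** A query tied to one visit reaches only those who attend it. Participants who withdraw, cannot be reached or are too ill to come would have no scheduled AE contact after randomization. The record does not fill the gap as written, because adjudication presupposes a known event and hospitalizations are abstracted only for screening and baseline. Section 11.0 provides for AE numbers and rates to be reviewed by blinded group but states no denominator. If non-attenders are counted as event-free, the rates are too low.

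A separate question concerns waitlist participants. Their last scheduled AE query comes before their first use of Lumen, although an event caused by that use would meet the plan's own AE definition.

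**Working it through.** The plan states no figure for AE ascertainment or AE risk, so there is none to reproduce. Assumed values are marked.

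**1. Scheduled queries after randomization.** Week 0 precedes allocation, weeks 1 to 12 are not applicable, and week 16 is at Visit 2. That leaves one. Its window is 112 − 14 = day 98 to 112 + 14 = day 126.

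**2. Participants without it.** Number = N × (1 − retention), with N = 60 (40 Lumen, 20 waitlist).
- 85%: 60 × 0.15 = 9 (6 and 3 if proportional)
- 90%: 6
- 95%: 3

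Because 85% is a floor, 9 is the figure at minimum retention and not an expected count.

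**3. Events among those 9 (assumed risk p).** Expected number = 9p. Chance of at least one = 1 − (1 − p)^9.
- p = 10%: 0.9 expected, chance 61%
- p = 20%: 1.8 expected, chance 87%
- p = 30%: 2.7 expected, chance 96%

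**4. Effect on the arm comparison.** Let both arms have true risk p = 20% (assumed), and let the m non-attenders in an arm of n have k times that risk (assumed). Events seen = np − mkp. Divide by n − m for the rate among those queried, or by n for the rate among those randomized. Differences are Lumen minus waitlist, and the truth is 0.

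| Missed, Lumen/waitlist | k | Lumen, queried | Waitlist, queried | Difference, queried | Difference, randomized |
|---|---|---|---|---|---|
| 6/3 | 2 | 5.6/34 = 16.5% | 2.8/17 = 16.5% | 0 | 0 |
| 9/0 | 1 | 6.2/31 = 20.0% | 4/20 = 20.0% | 0 | −4.5 points |
| 0/9 | 1 | 8/40 = 20.0% | 2.2/11 = 20.0% | 0 | +9.0 points |
| 9/0 | 2 | 4.4/31 = 14.2% | 4/20 = 20.0% | −5.8 points | −9.0 points |
| 0/9 | 2 | 8/40 = 20.0% | 0.4/11 = 3.6% | +16.4 points | +18.0 points |

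With proportional loss both rates fall below 20% but the difference stays at 0, and this also holds at k = 3. Bias between arms needs loss that differs by arm. If non-attenders have the same risk as attenders, using the number queried as the denominator removes it. The one-arm losses are extremes.

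**5. Waitlist use of Lumen (ceilings).** Up to 20 people could use Lumen with no AE query scheduled afterwards. If all 20 took it up and completed 8 sessions, that is 20 × 8 / (60 × 8) = 33% of Lumen sessions. With zero events seen, the one-sided 95% upper limit is 1 − 0.05^(1/n): 8.4% for the 34 Lumen participants queried at 85% retention, and 4.9% for 60. The 4.9% figure assumes full waitlist uptake and that all 60 are queried after use.

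**The case against.** The strongest case against is that the plan does not rely on the query alone. Section 7.0 provides PHQ9 item 9 alerts at each Lumen session and procedures for adverse events during scanning. Section 11.0 provides for staff trained to ascertain AEs, review of complaints, and IRB notice within 5 business days of learning of an unanticipated AE. The AE form is an interview, so nothing forbids giving it by phone. The visit window spans 28 days. The form and the cited Recruitment and Retention Plan are not in the documents. Both arms get the same query at the same time, and the study is described as minimal risk.

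Much of this stands. A reader might infer that non-attenders are never asked, or that AE data come only from completers. The documents support neither: they say only that no query is scheduled for non-attenders, and other channels can bring an event to light. But those channels depend on contact or on someone reporting the event, and the item 9 channel is scheduled during the trial only in the Lumen arm. They do not replace systematic ascertainment, and detection through them can differ by arm.

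A reader might also infer that people leave because they deteriorate, so that the arms look safer than they are. Appendix 3, B.4 does not say that. It raises, as possibilities, leaving after improvement and leaving for lack of it. That is reason to expect selective loss, without a known direction.

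**Conclusion.** The point holds as a gap in scheduled AE ascertainment that is cheap to close. After randomization there is one scheduled query, it depends on attending Visit 2, and at minimum retention up to 9 of 60 participants would not have it. Undercounting is likely if AE risk is anywhere near the assumed 10% to 30%. Bias in the arm difference is possible but conditional: it requires missed visits that differ by arm, and the plan gives no reason to predict which way.

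Three stronger readings are not supported.
- Waitlist use of Lumen does not contradict the claim of unbiased ascertainment. It lies outside the randomized comparison and is described as post-study, so it is a gap in safety coverage.
- It is not true that a third of Lumen users would contribute no AE data. Waitlist participants are due a query at week 16, and what is missing is data after their exposure. The 33% and 4.9% figures are ceilings.
- No AE rate feeds the decision to move to the R33 phase. That rests on neural target engagement (Appendix 3) and on the feasibility and acceptability milestones (Sections 1.0 and 3.0).

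The documents do not say whether the item 9 alerts continue when waitlist participants use Lumen.

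**What to change.** 1. In Section 11.0 and Appendix 2, give the same AE form by phone or REDCap, in the day 98 to 126 window, to every randomized participant who does not attend Visit 2. Report AE numbers and rates by arm with the number actually queried as the denominator, and show that number beside the number randomized.
2. Give waitlist participants who take up Lumen one AE query when they finish or stop, and tabulate it apart from the randomized comparison. Reconcile Section 7.0 (use after the end of the study) with Section 11.0 (monitor meetings and AE definition), so that the protocol says whether the safety monitoring plan covers that use. How clinical alerts are handled there is for the study team to state.
3. Reconcile Section 11.0, which mentions only the week 16 query, with the week 0 AE form in Appendix 2.

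The cost is up to about 9 calls at minimum retention, up to 20 further short queries with the existing form, and a change to the protocol wording.

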### Self-completed Ecological Daily Assessments (<3 minutes each day)

Using the Lumen companion application participants complete ecological end-of-day assessments of mood, stress, appraisal, and coping for 7 days every 2 weeks (over 16 weeks).

**Intervention Orientation.** Participants in the intervention arm attend a Lumen orientation visit (60 minutes) during which they will be given a Lumen intervention tutorial and receive a study iPad, configured to limit access to only the Lumen intervention enabled on the device. Before leaving participants are scheduled for the first PST session with Coach Lumen. As needed, Lumen intervention orientations can be done remotely.

**Intervention data collection.** Secure study iPads used by participants in the intervention arm are enabled with Lumen PST. Participants complete 8 PST sessions beginning with 4 weekly and then 4 biweekly intervals over 12 weeks on their assigned iPad. At the end of each PST session, participants are prompted to schedule their next session with Coach Lumen. They receive automated reminder notifications 1 day prior to their next session and on the session day and have the opportunity to make up missed sessions. Intervention participants also complete the PHQ9 and GAD7 and user experience surveys at all PST sessions. Upon completion of the intervention participants will receive a certificate of completion signed by [name]. They may also complete a post-intervention interview via Zoom to characterize participant perspectives regarding their Lumen use experience.

**Intervention fidelity assurance.** All PST sessions that participants complete with Lumen are audiorecorded. Session recordings and transcripts are stored on the Amazon Web Services (AWS) in study configured accounts, with coded identifiers (see Section 7.). These materials will be used to evaluate treatment fidelity and user-Lumen interaction.

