## **7.0 Expected Risks/Benefits**

This is a minimal risk study with prudent measures in place to protect the health and well-being of research participants and their privacy and confidentiality. Risks associated with participation in this study may include the potential for the following:

- Potential for self-harm
- MRI-related injury, discomfort, and distress (Aim 2: pilot RCT only)
- Patient privacy and confidentiality breach
- Accidental recording.

These risks are largely associated with the characteristics of the patient population to be studied and the procedures involved in the research. The target population includes patients with moderate, untreated depressive and/or anxiety symptoms. The risks are reasonable in relation to the anticipated benefits and are minimized by using procedures that are consistent with sound research designs and established research and clinical protocols. The following measures are implemented to minimize potential risks to participants in the study.

**Protection against risks of self-harm.** Some of the questions about depression, thoughts of death and other psychological symptoms and conditions as a part of study assessments may cause discomfort for some participants. However, in general the questions are not particularly intrusive or distressing, and stress is likely transient. In addition, participants are free to refuse to answer any questions. It is widely accepted that asking questions about thoughts of death or suicide does not lead to increased risk of suicide. Nevertheless, in the event that a patient is identified as being suicidal during the screening or follow-up phase of the study, the following self-harm protection protocol (adapted from the UIC IRB

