approved ENGAGE-2 study #2018-1174), is in place to immediately alert the study supervising psychiatrist to assess the patient’s suicidal thoughts by telephone, followed by notification of the participant’s PCP and appropriate clinical action if necessary. If a participant responds “1” (“several days”), “2” (“more than half the days”), or “3” (“nearly every day”) to the PHQ-9 question “Over the last 2 weeks, how often have you been bothered by thoughts that you would be better off dead or thoughts of hurting yourself in some way?”, we further assess the participant’s level of risk by asking “Do you have a plan for how you would commit suicide?” and then follow the protocol based on the assessed level of risk. Individuals reporting suicidal ideation on PHQ9 with an active plan at eligibility screening are excluded from participation. Nonetheless, the risk of emergent suicidality still exists after enrollment. Risk for suicide may be detected when a participant completes the PHQ9 at the beginning of each PST session with Lumen. Participants who score 1-3 (see above) on item 9 of the PHQ9, will be offered the option to call an emergency contact, the national [name]/[name] hotline, or 911 at the time of detection. This information is a pre-programmed script for Lumen. The supervising study psychiatrist, [name], the intervention manager, [name], receive immediate notifications, as outlined in the table below. The study psychiatrist calls the participant within 3-4 days to conduct an assessment, assess need for further referral, and discuss referral options depending on urgency, needs and preferences, available supports in place, insurance status and routine source of care. The study psychiatrist may refer the participant for immediate comprehensive evaluation (e.g., at a local emergency department), ambulatory psychiatric services, or community resources, with personal accompaniment depending on the evaluation outcome.

[If PHQ9 completed with SPEAC study staff by phone]	

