We will have a study doctor contact you within 3-4 days. In the meantime, do not delay seeking medical attention.

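### After randomization, PHQ9 item 9 and its psychiatrist alert are scheduled only at Lumen sessions, so the waitlist, and Lumen participants who stop attending or have finished session 8, have no scheduled suicidality screen through visit 2

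*Combined protocol and SAP*

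**What the plan says.** **Scope of the self-harm protocol.** Section 7.0 puts it in place "in the event that a patient is identified as being suicidal during the screening or follow-up phase of the study", without limiting it to one arm, and accepts that "the risk of emergent suicidality still exists after enrollment". The trigger is a score of 1 to 3 on PHQ9 item 9, which begins "Over the last 2 weeks, how often have you been bothered by thoughts that you would be better off dead". A positive answer leads to a call from the study psychiatrist. The online version tells the participant: "We will have a study doctor contact you within 3-4 days".

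**When item 9 is asked after enrollment.** Section 7.0 names one occasion: "Risk for suicide may be detected when a participant completes the PHQ9 at the beginning of each PST session with Lumen". Section 6.0 (intervention data collection) agrees: "Intervention participants also complete the PHQ9 and GAD7 and user experience surveys at all PST sessions". Appendix 2, footnote b, gives the PHQ9 two uses, eligibility screening before week 0 and progress monitoring at PST sessions. The schedule marks it NA at week 16, where HADS is the symptom outcome. Section 7.0 (Aim 2 privacy protections) lets waitlist participants take up Lumen only after the week 16 assessments.

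**Adverse events.** Section 11.0 counts a psychological event as an AE if it is a new symptom or a worsening of an existing condition. On ascertainment it says: "To ensure unbiased ascertainment, AEs will be systematically identified by querying participants at 16-week follow-up visits using the AE Patient Query Form". The blinded contact PI, biostatistician and safety monitor "will review summaries of the numbers and rates of all AEs by blinded treatment group". Neither section says whether an item 9 alert becomes an AE record.

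**The concern.** The PHQ9 does two jobs here: it tracks progress in therapy, and its item 9 is the trigger for the self-harm protocol. Tying it to therapy sessions suits the first job but not the second. The waitlist arm is 20 people not in treatment at entry, with PHQ9 scores up to 19. Only ideation with an active plan excludes them. If ideation emerges or worsens after screening, nothing scheduled would bring it to the psychiatrist's attention before the comparison ends. The same holds for Lumen participants who drop out of sessions, and for all of them between session 8 and visit 2. What is at stake is participant safety. AE rates do not enter the criteria for moving to the R33 phase.

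A second, smaller matter is that the AE section does not say how session alerts relate to the AE counts reviewed by group.

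**Working it through.** **1. The plan's own count.** Appendix 3, B.3.c, gives 8 PHQ9 occasions. The listed weeks 1, 2, 3, 4, 6, 8, 10 and 12 make 8, so the figure is reproduced.

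**2. Scheduled item 9 screens from randomization through visit 2.**
- Lumen, all sessions completed: 40 × 8 = 320.
- Lumen, acceptability targets just met (at least 95% complete 1 session, at least 80% complete 4): 38 people complete 1 or more and 32 of them complete 4, so 32 × 4 + 6 × 1 = 134.
- Waitlist: 20 × 0 = 0.

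**3. Could another measure stand in?** The measures Appendix 2 schedules for the waitlist after randomization include HADS, the worry, affect, problem-solving and dysfunctional-attitude scales, functioning, quality of life and the daily items on mood, stress, appraisal and coping. Section 7.0 attaches a self-harm alert to none of these. The week 16 AE query could pick up ideation if a participant volunteers it, but the form is not reproduced.

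**4. Longest time from last item 9 to visit 2, waitlist.** Inputs from Appendix 4: initial screen to visit 1, at most 28 days preferred, with rescreening required beyond 90; eConsent to visit 1, at most 14; visit 1 to randomization, at most 10; randomization to visit 2, 112 ± 14, so 98 to 126.

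| Item 9 last asked at | Days to visit 2 |
|---|---|
| Initial screening, preferred window | 28 + 10 + 126 = 164 |
| Initial screening, rescreen limit | 90 + 10 + 126 = 226 |
| Eligibility interview after eConsent | 14 + 10 + 126 = 150 |
| Visit 1 | 10 + 126 = 136 |

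The third row applies if the final eligibility questions in Section 5.0 repeat the PHQ9. The fourth applies if the week 0 mark in Appendix 2 means a PHQ9 at visit 1; footnote b suggests it means screening. In that fourth case the shortest gap is about 7 + 98 = 105 days, because the first week of daily assessments comes before randomization.

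**5. Lumen after session 8.** Appendix 4 puts session 8 in weeks 12 to 14 and visit 2 in weeks 14 to 18, so the unscreened tail is 14 − 14 = 0 to 18 − 12 = 6 weeks. For someone who stops attending, it runs from the last session attended.

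**6. What a week 16 item would cover.** Item 9 looks back 2 weeks: 14 of 112 days at the target visit date, or 12.5% of follow-up.

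**7. Calls generated.** Retained at 85%: 0.85 × 60 = 51. At an assumed 5% to 20% scoring 1-3: 51 × 0.05 = 2.6 and 51 × 0.20 = 10.2, so about 3 to 10.

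**8. AE rates, illustration only.** The documents give no ideation rate and no sensitivity for either source. Assume equal true risk, a query that finds a share q of events among the 85% retained, and session alerts that independently find a share d. Detection is b = 0.85q on the waitlist and a = 1 − (1 − b)(1 − d) in Lumen. With q = 0.5 and d = 0.6: b = 0.425, a = 1 − 0.575 × 0.4 = 0.770, a/b = 1.81. Varying q over 0.3 to 0.9 and d over 0.4 to 0.8 gives 1.12 to 3.34. If only the query is counted, the ratio is 1.0.

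**The case against.** The PHQ9 was chosen as a session progress measure and HADS as the independent outcome, so unequal PHQ9 schedules are deliberate. That stands for efficacy. It does not answer the safety point, because item 9 is also the protocol's trigger and the protocol is meant to operate during follow-up.

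The waitlist is not without protection. Ideation with an active plan excludes a person, scores of 1 to 3 at screening lead to a doctor's call whichever arm follows, people scoring 10 or more on the PHQ9 or GAD7 are offered resources, and participants may start outside treatment without being withdrawn. This lowers the risk. But these measures act at screening or depend on the participant's initiative; none is a screen during follow-up.

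A single item at week 16 leaves most of the gap open. That also stands. Screening the waitlist during weeks 2 to 12 would close more of it but would make the control less passive for the symptom and neural outcomes. That is a design trade-off for the sponsor.

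On AEs, the only systematic source named is the week 16 query, which runs in both arms and is justified in the plan as the route to unbiased ascertainment. The query form and staff training may already settle how alerts are handled. This objection succeeds against any claim of bias and leaves only a request for clarification.

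**Conclusion.** The screening gap is real and follows from the schedule without any assumed rate: up to 8 item 9 screens per Lumen participant after randomization, none per waitlist participant, and none at week 16 in either arm. The waitlist gap reaches 164 days on the preferred windows and 226 at the rescreening limit, provided item 9 is last asked at initial screening. The text does not settle whether it is repeated later; if it is, the longest gap is 150 or 136 days.

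A reader might go further and infer that suicidality-type AE rates will be biased so that Lumen looks worse. The documents do not support that. It requires session alerts to be counted in the by-group AE rates, which no section says. The ratios in step 8 come from assumed inputs and carry no weight in judging how serious this is. What the documents do show is an unstated rule, worth one clarifying passage.

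**What to change.** **Main change (Appendix 2 and Section 7.0).** Give PHQ9 item 9 to both arms at week 16, with the existing online self-harm message and psychiatrist call. Place it after the outcome surveys and the AE query, so that it cannot influence either. The cost is one question for up to 60 participants and about 3 to 10 calls on the assumption in step 7. It covers only the preceding 2 weeks and does not recover earlier episodes.

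**Clarification (Section 11.0).** Record the source of each AE (week 16 query, PHQ9 alert, other) and base by-group AE rates on the week 16 query. List alerts judged to be new or worse ideation as AEs outside that comparison. Have the study psychiatrist, who under Section 11.0 may become unblinded, review them as they occur, so that an excess specific to Lumen is not hidden. This needs wording and one field on the AE form.

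Item 9 for the waitlist during weeks 2 to 12 is not part of this recommendation.
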